7.5.1 Objective response rate (ORR)

Objective response rate is defined as the percentage of patients who have best overall response of CR or PR prior to any evidence of progression (as defined by RECIST 1.1).

A visit response of CR is defined when all TL and NTL lesions present at baseline have disappeared (with the exception of lymph nodes which must be < 10 mm to be considered non-pathological) and no new lesions have developed since baseline. A visit response of PR is defined when the sum of diameters of the TLs has decreased by 30% or more compared to baseline (with no evidence of progression) and the NTLs are at least stable with no evidence of new lesions. A confirmed response of CR/PR means that a response of CR/PR is recorded by two consecutive visits with ≥ 4 weeks' time interval.

When the investigator is in doubt as to whether progression of disease has occurred and therefore reassesses the patient at a later date, the date of the initial scan should be declared as the date of progression if the repeat scans confirm progression.

Any CR or PR which occur after a further anticancer therapy is received will not be included in numerator of the ORR calculation.

Best overall response (BOR) will be calculated as the best response recorded from study treatment starts until RECIST assessed progression is documented for each patient, prior to any subsequent cancer therapy received and irrespective of whether patients discontinued treatment of DZD9008. When confirmation of CR/PR is required, BOR of CR or PR will only be claimed only if the criterion for confirmed response is met. When SD is believed to be the best response, at least 6 weeks from baseline (with \pm 7 day visit window) is required.

Date: July 24,2023

7.5.2 Progression Free Survival (PFS)

PFS is defined as the time from date of first dosing until the date of objective disease progression as defined by RECIST 1.1 or death (by any cause in the absence of progression) regardless of whether the subject withdraws from the study treatments or receives another anticancer therapy prior to progression.

Patients who have not progressed or died at the time of analysis will be censored at the time of the latest date of assessment from their last evaluable RECIST assessment. If the patient progresses or dies after two or more consecutively missed RECIST assessments visits, the patient will be censored at the time of latest evaluable RECIST assessment before the missed visit. If the patient has no evaluable visits or does not have baseline data they will be censored on the first dosing date unless they die within two RECIST assessment visits after baseline.

If a patient discontinues treatment prior to progression and/or receives a subsequent therapy prior to progression then these patients will continue to be followed until evidence of objective disease progression as defined by RECIST 1.1 and their PFS time will be derived as defined above.

The PFS will always be derived based on scan/assessment dates not visit dates.

Note: Symptomatic deterioration will not be regarded as a progression event.

7.5.3 **Duration of Response (DoR)**

Duration of response will be defined as the time from the date of first documented response, that is subsequently confirmed until the date of documented progression or death in the absence of disease progression, the end of response should coincide with the date of progression or death from any cause used for the PFS endpoint. The time of the initial response will be defined as the latest of the dates contributing towards the first visit response of PR or CR.

If a patient does not progress following a response, then his/her duration of response will use the PFS censoring time.

7.5.4 Disease control rate (DCR)

Disease control rate is defined as the proportion of patients with a best overall response of CR, PR or SD.

7.5.5 Change in tumor size

Tumor size is defined as the sum of the lengths of the longest diameters of the RECIST 1.1 target lesions. Percentage change in tumor size will be determined for patients with measurable disease at baseline and is derived at each visit by the percentage change in the sum of the diameters of TLs compared to baseline.

For further details see Appendix F of this Clinical Study Protocol.

7.5.6 Overall Survival (OS)

Overall survival will be assessed based on the date of first dose and survival status at the time of analysis.

Overall survival is defined as the interval between the date of first dose and the date of patient death due to any cause. Patients who have not died at the time of the statistical analysis will be censored at the time they were last known to be alive.

7.6 Calculation of patient reported outcome (PRO)

7.6.1 EQ-5D-5L

The EQ-5D-5L index comprises 5 dimensions of health (mobility, self-care, usual activities, pain/discomfort and anxiety/depression). For each dimension, respondent select which statement best describes their health on that day from a possible 5 options of increasing levels of severity (no problems, slight problems, moderate problems, severe problems and unable problems). A unique EQ-5D health state is referred to by a 5-digit code allowing for a total of 3125 health states. For example, state 11111 indicates no problems on any of the 5 dimensions. In addition to the descriptive system, respondents also assess their health on the day of assessment on a visual analogue scale, ranging from 0 (worst imaginable health) to 100 (best imaginable health). The score is reported separately.

7.7 Calculation or derivation of exploratory research variables

Results from the exploratory biomarker and pharmacogenetic research etc.may be reported separately from the Clinical Study Report for the main study.

7.8 Analysis sets

The analysis of data will be based on different subsets according to the purpose of the analysis. Throughout the safety result sections, erroneously treated patients (eg, those assigned to receive dose A who actually received dose B, those who failed to meet the selection criteria) will be accounted for in the actual dose group received.

Table 10 Analysis set definition

Analysis Set	Definition
All patients	All patients screened
All randomized patients	All patients who were randomized (applicable for Part B only)
Safety	All patients who received at least 1 dose of DZD9008
Full analysis set (FAS)	All randomized NSCLC patients with documented EGFR Exon20ins mutation in tumor tissue who were previously treated with platinumbased chemotherapy, received at least 1 dose of DZD9008 and have measurable disease at baseline as identified by IRC (applicable for Part B only)
Centrally confirmed EGFR Exon20ins by tumor tissue	All patients in full analysis set with EGFR Exon20ins mutations confirmed in tumor tissue by central laboratory (applicable for Part B only)
Centrally confirmed EGFR Exon20ins by plasma ctDNA	All patients in full analysis set with EGFR Exon20ins mutations confirmed in plasma ctDNA by central laboratory (applicable for Part B only)

Analysis Set	Definition
Pharmacokinetics	All dosed patients who has at least one measurable plasma concentration of DZD9008 post dose with no protocol deviations or AE thought to impact the analysis of the PK data
Food effect	Patients from the food effect cohort for whom a PK profile is available on at least one of the fed and fasted dosing days
Evaluable for response	Dosed patients with measurable disease at baseline and follow up RECIST assessment (Part A)
Exploratory biomarkers	All patients that participate in the exploratory biomarker research
Paired biopsy (PoM cohort)	Dosed patients with a pre-study tumor biopsy and one tumor biopsy on study treatment

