7. EVALUATION AND CALCULATION OF VARIABLES AND STATISTICAL METHODS

7.1 Definition of study endpoints

In Part A, the primary endpoints for determining the MTD and RP2D are the incidence of dose-limiting toxicities (DLTs), adverse events (AEs), serious adverse events (SAEs) and abnormal laboratory test results. The RP2D definition will be based on integrated analysis of PK, tolerability or anti-tumor efficacy data.

The secondary and exploratory endpoints are as following:

- PK assessment includes concentrations of DZD9008 in plasma and/or urine of individual patient (secondary).
- Preliminary assessment of anti-tumor efficacy includes the objective response rate (ORR), which includes the number of CR and PR based on RECIST 1.1, disease control rate (DCR), and duration of response (DoR) (secondary).
- The effect of food on PK of DZD9008 (secondary).
- To retrospectively assess anti-tumor activity of DZD9008 in patients with EGFR Exon20ins according to RECIST 1.1 by Independent Review Committee (IRC) (secondary).
- Retrospective confirmation of EGFR or HER2 Exon20ins in archived tumor tissue or fresh tumor biopsy or plasma sample (exploratory).
- Metabolite identification (exploratory).
- Other biomarkers (exploratory).
- To explore the relationship between DZD9008 exposure and selected endpoints.

In Part B, the primary endpoints for determining anti-tumor efficacy is ORR according to RECIST 1.1 by Independent Review Committee (IRC).

Clinical Study Protocol Drug Substance: DZD9008 Protocol No.: DZ2019E0001

Edition Number: 12.0 Date: July 24,2023

The secondary and exploratory endpoints are as following:

- Safety and tolerability, including adverse events (AEs), serious adverse events (SAEs) and abnormal laboratory test results (secondary).
- PK assessment includes concentrations of DZD9008 in plasma of individual patient (secondary).
- Additional anti-tumor efficacy endpoints include BOR, DOR, PFS and overall survival (OS) (secondary).
- Collect and store tumor samples for companion diagnostics development and potential future exploratory research that may influence the development of DZD9008 (exploratory).
- To collect and store plasma samples for EGFR Exon20ins mutation testing and necessary technical studies for liquid biopsy companion diagnostic development and approval (exploratory).

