7.9.7.1 Tumor response

The analysis population will be the evaluable for response analysis set for Part A and FAS for Part B.

Summaries of the number of patients with best overall response in each part will be provided in the following categories: Complete Response (CR), Partial Response (PR), Stable Disease (SD), Progressive Disease (PD) and Non-Evaluable (NE). Objective response rate and disease control rate will be summarized.

For Part B, p value for the test against the null hypothesis of ORR \le 17\% will reported based on the Simon's two-stage method. ORR and two-sided 97.5\% CI will be calculated based on Jung's method (26) to adjust the bias caused by optional sampling in the Simon's two-stage design and provide the uniformly minimum variance unbiased estimator.

Date: July 24,2023

Data will be analyzed by subgroup (e.g. taken into consideration of the prior treatment) in Part B.

7.9.7.2 **Duration of response**

The analysis population for duration of response will be the subset of the evaluable for response population (Part A) or FAS (Part B) with a best overall response of confirmed CR/PR. Duration of response will be summarized and the number (%) of responding patients with a duration of response > 3, > 6, > 9 and > 12 months will be presented. Or if data are appropriate, response ongoing rates at 6, 9 and 12 months will be estimated based on Kaplan-Meier method. A Kaplan Meier plot and median duration of response (calculated from the Kaplan-Meier) will be presented.

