7.9.7.4 Progression free survival

The analysis populations for PFS will be the safety analysis set for Part A and FAS for Part B.

PFS will be displayed using a Kaplan-Meier plot. The progression-free survival rates at 6, 9 and 12 months (calculated from the Kaplan-Meier estimator), median and quartiles (if estimable from the Kaplan-Meier estimator) will be summarized.

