Archival tumor tissue or fresh biopsy (mutation confirmation)	X							6.6.2
Vital signs	X	X	X	X	X	X		6.3.3
Height	X							6.3.3
Weight	X	X			X	X		6.3.3
ECG	X	X	X	X	X	X		6.3.5
Clinical chemistry/ Hematology/Urinalysis	×	×	×	×	X	X		6.3.4
HBV/HCV/HIV/COVID-19 ^d	×							4.2

Assessment	Screen)	Cycle 1 (21 days)		Cycle 2 (21 days) onwards	Discontinuation	28-day follow up	Details in section
Day	-28 to -1	1 h	в8	15 ^a	1^{b}			
APTT/INR	×	×	×	×	×	×		6.3.4
Echocardiogram/MUGA °	×	V		On (←On Cycle 3 Day 1, then every 6 weeks→	↑		6.3.5.2
Lung function test (LFT) °	×	V		On	← On Cycle 3 Day 1, then every 6 weeks	↑		6.3.5.3
PRO-CTCAE and FACIT GP5 questions		×	X	X	Weekly until the end of cycle 6, then on day 1 of each cycle	X		6.9.2 & 6.9.3
PK blood samples		*X	X	X	$_{*}$			6.5.1.2
Blood sample for ctDNA & exploratory Biomarkers (optional)	Х	X	X	X	X (C2D1-C6D1 and continuous every even cycle D1 until disease progression)	very even cycle D1 until	l disease	6.6.2
RECIST assessments ^f	×		↓		\leftarrow On Cycle 3 Day 1, then every 6 weeks	eks		6.8.1
Dose with DZD9008				→	←X (daily dosing)X	^		5.1.2
Concomitant medication	*				X	←		4.3.1
Adverse events 8	*				←	^		6.4

#: multiple time point for PK sampling. Hospitalization can be allowed for out of business time PK collection.

- a. ±1-day visit window is allowed for C1D8 & D15.
- b. All study visits from Cycle 2 Day 1 onwards may be performed within a visit window of \pm 2 days.
- c. Pregnancy test needs to be within 7 days of the first dosing.
- d. HBV/HCV/HIV/COVID-19 test can be done based on local practice.
- e. Echo/MUGA and LFT needs to be done within 14 days of the first dosing.
- CT is preferred. Same scan modality is required to use for tumor scan and RECIST assessment from baseline till follow up for one patient. Please refer to Appendix F of CSP about the details of RECIST assessment. ij
- AE will be collected from the first dosing of DZD9008; SAE is required to be collected from inform consent ьio

^{*:} Day 1 of Cycle 2, 3, 4

- h. For CID1, -1 day window is allowed for laboratory safety testing and physical examination
- Eye examination includes: Visual acuity, Pupils, Intraocular pressure, External examination, Slit-lamp examination, and Fundoscopic examination (pupil dilate is not required) and others if clinically indicated. . _:
- PRO-CTCAE and FACIT GP5 questionnaire will be collected weekly for the first 18 weeks (to cycle 6), and then on day 1 of each subsequent cycle (expansion cohort 3-6).

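### Part A response and disease control rates leave out dosed patients who never have a follow-up scan, so both rates can only be biased upward

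*Protocol*

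**What the plan says.** Table 10 in Protocol section 7.8 gives the Part A evaluable-for-response set three conditions: dosing, measurable disease at baseline, and a follow-up RECIST assessment ("Dosed patients with measurable disease at baseline and follow up RECIST assessment (Part A")). Section 7.9.7.1 applies it: "The analysis population will be the evaluable for response analysis set for Part A and FAS for Part B." The same section continues: "Objective response rate and disease control rate will be summarized."

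Both rates are proportions of patients, so the analysis set is the denominator. Section 7.5.1 states: "Objective response rate is defined as the percentage of patients who have best overall response of CR or PR prior to any evidence of progression." Section 7.5.4 states: "Disease control rate is defined as the proportion of patients with a best overall response of CR, PR or SD."

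In the expansion cohorts the first follow-up assessment is scheduled as "On Cycle 3 Day 1, then every 6 weeks" (Table 13).

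Two neighbouring rules differ:

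- For progression-free survival (PFS), section 7.9.7.4 says: "The analysis populations for PFS will be the safety analysis set for Part A and FAS for Part B." No scan is needed to be counted.
- The Part B full analysis set in Table 10 has no follow-up-scan condition. SAP Table 1 scores death before the first RECIST assessment as NE, which keeps the patient in the denominator.

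**The concern.** Entry to the Part A response set depends on something that happens after dosing. The people most likely to fail that condition are early failures, above all those who die before the first scan. They cannot have a response or disease control, so removing them lowers the denominator and leaves the numerator alone.

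The protocol is also inconsistent with itself. Under section 7.5.2, a Part A patient who dies without a scan within two assessment visits of baseline is a PFS event, yet the same patient disappears from ORR and DCR. Section 7.9.7.1 plans an NE category for each part, but in Part A the unscanned patients are removed before they can be placed in it.

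What is at stake is the accuracy of the Part A rates. Section 7.1 gives efficacy a role in choosing the dose: "The RP2D definition will be based on integrated analysis of PK, tolerability or anti-tumor efficacy data." Sections 5.1.4 and 5.2.4 also use early-phase response rates to describe activity relative to other agents.

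**Working it through.** **Planned size.** No power or precision is stated for Part A response. The only planned figure near this denominator is enrolment, which reproduces:

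- Expansion cohorts 1 to 6 (section 3.1): 10 + 10 + (10 to 20) + (10 to 20) + 30 + 20 = 90 to 110.
- With about 30 in escalation and 10 in food effect (section 7.2.1): 130 to 150, as stated.

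**Timing of the first scan.** Cycle 3 Day 1, counted from the first dose with the cycle lengths in Tables 11 to 13, each with a window of 7 days either way:

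- Expansion: 21 + 21 + 1 = day 43.
- Escalation: 8 + 28 + 21 + 1 = day 58.
- Food effect: 16 + 21 + 21 + 1 = day 59.

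**Direction and size.** Let N be dosed patients with measurable disease, R those with the outcome (response, or disease control), and d those with no follow-up scan. None of the d can be in R. The all-dosed rate is R/N and the plan's rate is R/(N-d). Their ratio is 1/(1-f) with f = d/N, which exceeds 1 whenever d > 0 and R > 0.

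The documents do not give f, so the values below are assumptions. The 25% is the one unredacted response rate by dose (400 mg, section 5.1.4), treated here as if it were the all-dosed rate. That section does not say whether it is Part A alone or pooled with study DZ2019E0002. The 80% DCR is assumed.

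| Assumed f | Factor 1/(1-f) | ORR 25% reads | DCR 80% reads |
|---|---|---|---|
| 5% | 1.053 | 26.3% | 84.2% |
| 10% | 1.111 | 27.8% | 88.9% |
| 15% | 1.176 | 29.4% | 94.1% |

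In a cohort of 20 with two patients unscanned, 5/20 (25.0%) becomes 5/18 (27.8%), and 16/20 (80.0%) becomes 16/18 (88.9%).

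**Is an f of this order plausible from deaths alone?** The Introduction quotes a median overall survival of about 24 months on chemotherapy. Assuming exponential survival, P(death before the scan) = 1 - exp(-ln 2 × t / median), with t in months (days/30.4375):

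- Median 24 months: 3.9% by day 43 (t = 42/30.4375) and 5.3% by day 58 (t = 57/30.4375).
- Assumed median 12 months: 7.7% and 10.3%.

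These give factors of about 1.04 to 1.11. This is a scale only. Withdrawals without a scan would add to it, and the entry criteria (performance status 0 to 1, life expectancy of at least 12 weeks) would reduce it.

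**The case against.** The case for leaving this alone has real strength.

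- **Scans are meant to continue.** A reader might infer that every patient who stops for toxicity or worsens clinically before the first scan leaves the denominator. The documents do not support that. Section 5.3 (for Part A expansion), section 6.3.6.2 and Appendix F (symptomatic deterioration) ask for RECIST assessments to go on until objective progression. Such patients drop out of the set only if no later scan is done. This stands and narrows the mechanism.
- **Dose choice.** A reader might infer that the rule favours more toxic doses. That requires toxicity stops to go unscanned, contrary to the sections just cited. Section 7.1 also names dose-limiting toxicities, adverse events and laboratory abnormalities as the primary endpoints for the dose decision, and adverse events are summarized in all dosed patients (section 7.9.3). Sections 3.2.2 and 5.1.4 show that both Part B doses had already been selected.
- **Comparison with Part B.** A reader might infer that the two parts' rates will be shown side by side on different denominators. Section 7.9 says that the two parts are reported separately.
- **Visibility.** Early failures can still be seen through PFS, the listing of deaths and the listing of discontinuation reasons. This stands, but it does not correct ORR or DCR.
- **Size.** For 5/20 the exact 95% interval is 8.7% to 49.1%, so a shift of 2.8 points is small beside sampling error. This stands for a single cohort. The bias nevertheless always runs the same way and does not shrink as cohorts are combined.
- **Unseen plan.** SAP section 1 says that Part A has its own analysis plan. It was not available and may already contain an all-dosed analysis.

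**Conclusion.** The point holds as a limited one. As the protocol is written, Part A ORR and DCR exclude dosed patients with measurable disease who are never scanned after baseline. The upward direction follows from arithmetic alone. The size does not: it depends on f, which the documents do not give, and it is zero if every such patient had a follow-up scan. For f between 5% and 15%, the inflation is about 5% to 18% of the true rate. That is roughly 1 to 4 points on an ORR of 25%, and 4 to 14 points on a DCR of 80%.

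These endpoints are secondary and preliminary. It would be wrong to read the point as touching the pivotal result, because the Part B full analysis set needs no follow-up scan.

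**What to change.** For Part A ORR, DCR and best overall response, use all dosed patients with measurable disease at baseline. Count those without a follow-up scan as NE and keep them in the denominator, as Part B does. State how many there are, by dose group.

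Keep the current evaluable set as a supplementary display and for change in tumor size (section 7.9.7.3), where a post-baseline measurement is needed. This calls for an added set in Table 10 and matching edits to sections 7.9.7 and 7.9.7.1, not a redefinition of the existing set. The separate Part A analysis plan should be aligned.

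The cost is slightly less favourable Part A rates wherever patients went unscanned, and one extra table. Part A rates had already been analysed at the April 2023 cut-off (section 2.3.5), so the change should be labelled as made after those results were seen. No new data or patients are needed.

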7.9 Methods of Statistical analysis

The statistical analyses will be performed by Dizal statistical group or designated third party provider, under the direction of Dizal. Data from Part A and Part B will be provided separately. Summary statistics will be presented by dose group in Part A and by study cohort in Part B.

7.9.1 Demographic data

Characteristics of the patients, including medical history, disease characteristics at baseline, prior and concomitant medications will be listed for each patient and summarized.

Reasons for discontinuation of investigational product will be listed including the day of treatment discontinuation and will be summarized.

7.9.2 Exposure

Dose administration data for the investigational product, including the cycle number, start/end dates, dose (unit), dose modifications will be listed for all patients in the safety analysis set.

Total exposure duration (date of last dose minus date of first dose + 1, regardless of any intermittent interruptions) and the total administered dose, as well as treatment compliance will be summarized by the following: mean, standard deviation, minimum, maximum, median and number of observations. In addition, the number and percentage of patients with at least one dose interruption and at least one dose reduction will be presented separately for the initial period defined as 21 days of multiple dosing (cycle 1) and for any time following this initial period of the study.

